14.4. Compliance with the Protocol

All processes and procedures defined in this protocol will be adhered to. Emergency departures from the protocol that eliminate an apparent immediate hazard to a particular patient and that are deemed by the Investigator as crucial for the safety and wellbeing of that patient may be instituted for that patient only and documented as deviations. The Investigator will contact the medical monitor as soon as possible regarding such a deviation. These departures do not require preapproval by the IRB/IEC; however, the IRB/IEC and Medical Monitor must be notified in writing as soon as possible in accordance with the IRB/IEC policies after the departure has been made.

14.5. Confidentiality

14.5.1. Data

All information regarding the nature of the proposed investigation that is provided to the Investigator by the Sponsor, the Sponsor's designee, or the study monitor, with the exception of information that is required by law or regulations to be disclosed to the IRB/IEC, the patient's parent(s) or legal guardian(s) or the appropriate regulatory authority, must be kept in confidence by the Investigator in accordance with current Health Insurance Portability and Accountability Act (HIPAA) standards and/or European standards.

14.5.2. Patient Confidentiality

The anonymity of participating patients will be maintained to the extent required by applicable laws and in accordance with current HIPAA standards. Patients may be referenced by their initials and an assigned patient identification number on the CRFs and other data collected by the Sponsor. The Investigator must maintain all documents related to the study that identify the patient (e.g. the signed informed consent document) in strict confidence, except to the extent necessary to allow auditing by the appropriate regulatory authorities, the IRB/IEC, the study monitor, or the Sponsor or its representatives.

15. STUDY DOCUMENTATION AND GENERAL INFORMATION

15.1. Essential Study Documents

Essential study documents are among the critical documents required before study enrollment is to occur. Essential documents, as well as supplemental information such as the Investigator's Brochure, Pharmacy Manual, CRF Completion Guidelines, final protocol, as specified in the Clinical Operations Manual and/or Regulatory Binder, must be kept on-site in a designated study site file.

The study site files will also contain, including but not limited to, patient accountability records, drug accountability (receipt/dispensing) records, Sponsor/Investigator correspondence, IRB/IEC correspondence, deviations, biological sample records, and SAE and Investigational New Drug (IND) safety reports/Safety Alert Letters.

15.2. General Information

The Investigator should refer to the current Investigator's Brochure along with subsequent Safety Alert Letters, the Clinical Study Operations Manual, Pharmacy Manual, Laboratory Manual, CRF Completion Guidelines, and all other study-specific information that is provided during the study initiation visit or by the study monitor.

15.3. Dissemination of Study Results

The information that is developed during the conduct of this clinical study is considered to be strictly confidential. This information may be disclosed only as deemed necessary by Sarepta Therapeutics, Inc. However, at the conclusion of this clinical study, a clinical study report will be prepared. In addition, a manuscript will be prepared for publication in a reputable scientific journal under the direction of the Sponsor. Sarepta Therapeutics, Inc. will publish and communicate the clinical study results, irrespective of positive or negative findings. Data generated for this study will be exclusively owned by Sarepta Therapeutics, Inc., as detailed in the Clinical Trial Agreement. The study will be registered on ClinicalTrials.gov. After completion of the study, results will be disseminated through ClinicalTrials.gov.

15.4. Product Handling and Complaints Reporting

If there are any issues during the course of the study related to the quality of the IP, the Investigator, clinical site pharmacist or pharmacy designee should contact the Sponsor or designated contract research organization (CRO).

1. INTRODUCTION

This analysis plan summarizes the planned analyses and presentation of the safety and efficacy data from the Sarepta Therapeutics, Inc. Protocol 4658-204: "An Open-Label, Multi-Center Study to Evaluate the Safety and Tolerability of eteplirsen in Patients with Advanced Stage Duchenne Muscular Dystrophy".

The investigational product is eteplirsen injection. Eteplirsen 30 mg/kg will be administered as an intravenous (IV) infusion over approximately 35 to 60 minutes, or approximately 5 mL/min, once a week for up to 96 weeks, followed by a safety extension (not to exceed 48 weeks), until the product is commercially available or until patients can transition into another eteplirsen trial.

2. STUDY OBJECTIVES

The primary objective of this study is to explore safety and tolerability of eteplirsen in patients with advanced stage Duchenne muscular dystrophy (DMD) who are amenable to exon 51 skipping.

3. LIST OF ABBREVIATIONS AND DEFINITIONS OF TERMS

Abbreviation	Expanded Term
CCI	
AE	adverse event
ALT	alanine aminotransferase
AST	aspartate aminotransferase
BMI	body mass index
BUN	blood urea nitrogen
DMD	Duchenne muscular dystrophy
ECG	electrocardiogram
ЕСНО	echocardiogram
eCRF	electronic case report form
CC	
CCI	
GGT	gamma-glutamyl transferase
IV	intravenous
KIM-1	kidney injury molecule-1
LLN	lower limit of normal
CCI	
MedDRA	Medical Dictionary for Regulatory Activities
CCI	
PT	Preferred Term
CCI	
SAE	serious adverse event
SAP	Statistical Analysis Plan

SD standard deviation

SE standard error

SMQ standard MedDRA query

SOC System Organ Class

CCI

TEAE treatment-emergent adverse event

TEMA treatment-emergent markedly abnormal

ULN upper limit of normal

WHO World Health Organization

CCI

4. STUDY OVERVIEW

4.1. Study Design

This is an open-label, multi-center study to explore the safety and tolerability of eteplirsen injection in patients with advanced stage DMD with confirmed genetic mutations amenable to treatment by exon 51 skipping.

Patients will be evaluated for inclusion during a Screening/Baseline period of up to 4 weeks. Eligible patients will receive once weekly IV infusions of 30 mg/kg eteplirsen for up to 96 weeks. An extension period may be considered after the end of the 96-week planned dosing period.

Safety will be regularly assessed throughout the study via the collection of adverse events (AEs), laboratory tests, electrocardiograms (ECGs), echocardiograms (ECHOs), vital signs, and physical examinations.

4.2. Number of Study Sites

This study will be conducted at approximately 10 sites in the United States.

4.3. Overall Time and Events Schedule

The Schedule of Events is displayed in Tables 1 and 2. Greater detail concerning the schedule of events can be found in the protocol.

Table 1 Schedule of Events - Screening to End of Study

Study Period	Screening						Trea	tment P	eriod					
Week	up to Week -4	BL/1	4	8	12	16	20	24	28	32	36	40	44	48
Informed Consent	X													
Inclusion/Exclusion	X	X												
Medical History	X													
Full Physical Exam	X	X	X		X			X						X
Brief Physical Exam				X		X	X				X			
Vital Signs ^a	X	X	X	X	X	X	X	X	X	X	X	X	X	X
Weight	X	X	X	X	X	X	X	X	X	X	X	X	X	X
Safety Lab Assessments	X	X ^b	X	X	X			X			X			X
CCI														
Whole Blood (Genotyping CCI) ^c	X													
Height and Ulnar Length	X	X			X			X			X			X
CCI														
CCI														
ECG	X ^f				X			X			X			X
Holter ECG	X ^f													X
ЕСНО	X ^f				X			X			X			X

Version 1.0 (20 April 2017) Page 10 of 40

Study Period	Screening		Treatment Period										
Week	up to Week -4	BL/1	BL/1 4 8 12 16 20 24 28 32 36 40 44 48										
Study Drug Infusion			Once Weekly										
Conmed/Therapy						Сс	ontinuou	s					
AE Assessment						Сс	ntinuou	s					

Footnotes for Table 1 Schedule of Events: Screening through Week 48

Functional assessments, \overline{CCI} , ECG, Holter ECG, and ECHO have a ± 2 weeks window

- ^a For infusion visits, vital signs are to be collected within approximately 30 minutes prior to infusion and approximately 5, 30, and 60 minutes after the end of the infusion. If the patient has not experienced an infusion reaction after the first year of treatment, vital signs may be collected only 30 minutes after the end of the infusion.
- ^b Blood samples for the safety laboratory assessments must be obtained within 2 weeks prior to the Baseline/Week 1 visit, and results must be available prior to dosing at Baseline/Week 1. If more than 2 weeks have elapsed since the collection of blood samples for the Screening safety laboratory assessments, it must be repeated. If less than 2 weeks have elapsed since the collection of blood samples for the Screening safety laboratory assessments, additional safety laboratory assessments do not need to be performed.
- ^c Patients may start dosing based on local genotyping results provided that these results fulfill the required inclusion criteria; however, all patients must undergo genetic testing to confirm the exon 51 skippable mutation CCI.
- Screening ECG, Holter ECG, and ECHO may be performed at any time during the Screening period; however results must be available on Day 1, prior to dosing.
- g In the event of early termination prior to Week 96, the Week 96 assessments should be completed as the Early Termination Visit.
- ^h End of Study visit should occur within 4 weeks after last dose

Version 1.0 (20 April 2017) Page 11 of 40

Study Period					7	Гreatm	ent Per	riod					Safety Extension	End of Study ^h
Week	52	56	60	64	68	72	76	80	84	88	92	96/ET ^g	See Table 2	4 weeks after last infusion (as applicable)
Informed Consent														
Inclusion/Exclusion														
Medical History														
Full Physical Exam						X						X		X
Brief Physical Exam														
Vital Signs ^a	X	X	X	X	X	X	X	X	X	X	X	X		X
Weight	X	X	X	X	X	X	X	X	X	X	X	X		X
Safety Lab Assessments ^b						X						X		X
CCI														
Whole Blood (Genotyping/CCI) ^c														
Height and Ulnar Length						X						X		
CCI														
CCI														
ECG						X						X		
Holter ECG												X		
ЕСНО						X						X		
Study Drug Infusion							Once	Weekl	y					

Version 1.0 (20 April 2017)

Page 12 of 40

Study Period					7	[reatm	ent Per	iod				Safety Extension	End of Study ^h
Week	52	56	56 60 64 68 72 76 80 84 88 92 96/ET ^g last infusio					4 weeks after last infusion (as applicable)					
Conmed/Therapy		Continuous											
AE Assessment								С	ontinuo	us			

Footnotes for Table 1 Schedule of Events: Week 52 through End of Study

Functional assessments, \overline{CCI} , ECG, Holter ECG, and ECHO have a \pm 2 weeks window

- ^a For infusion visits, vital signs are to be collected within approximately 30 minutes prior to infusion and approximately 5, 30, and 60 minutes after the end of the infusion. If the patient has not experienced an infusion reaction after the first year of treatment, vital signs may be collected only 30 minutes after the end of the infusion.
- ^b Blood samples for the safety laboratory assessments must be obtained within 2 weeks prior to the Baseline/Week 1 visit, and results must be available prior to dosing at Baseline/Week 1. If more than 2 weeks have elapsed since the collection of blood samples for the Screening safety laboratory assessments, it must be repeated. If less than 2 weeks have elapsed since the collection of blood samples for the Screening safety laboratory assessments, additional safety laboratory assessments do not need to be performed.
- ^c Patients may start dosing based on local genotyping results provided that these results fulfill the required inclusion criteria; however, all patients must undergo genetic testing to confirm the exon 51 skippable mutation CCI.
- Screening ECG, Holter ECG, and ECHO may be performed at any time during the Screening period; however results must be available on Day 1, prior to dosing.
- g In the event of early termination prior to Week 96, the Week 96 assessments should be completed as the Early Termination visit.
- ^h End of Study visit should occur within 4 weeks after last dose

Version 1.0 (20 April 2017) Page 13 of 40

Table 2 Schedule of Events - Safety Extension Period

Study Period	Safety Extension Period (Starting at Week 97 and continuing until the product is commercially available or until patients can transition into a separate eteplirsen study)						
Week	120	144					
Full Physical Exam	X	X					
Vital Signs ^a	Wee	Weekly					
Weight	Every 4	Every 4 Weeks					
Safety Lab Assessments	X	X					
CCI							
CCI							
ECG	X	X					
ЕСНО	X	X					
Study Drug Infusion	Once V	Once Weekly					
Conmed/Therapy	Conti	Continuous					
AE Assessment	Conti	Continuous					

Functional assessments, CCI, ECG, Holter ECG, and ECHO have a ±2 weeks window

Version 1.0 (20 April 2017) Page 14 of 40

^a For infusion visits during the Safety Extension Period, vital signs are to be collected within approximately 30 minutes prior to infusion and approximately 5, 30, and 60 minutes after the end of the infusion. If the patient has not experienced an infusion reaction in the past year of treatment, vital signs may be collected only 30 minutes after the end of the infusion.

4.4. Analysis Variables

4.4.1 Subject Disposition

- Subjects not completing the study.
- Study drug exposure. This will be characterized by calculating, for each subject, the total amount of medication received during the study and the time in days between the first dose and the last dose.

4.4.2 Demographics and Baseline Characteristics

- Age, race, ethnicity, weight, height, body mass index (BMI), genotype for column ambulatory status, and column will be summarized.
- Age will be calculated at date of first dose of eteplirsen at the Week 1 visit
- For the purposes of the demographic summaries, weight will be the last available measurement taken before the first study drug administration.
- BMI will be calculated as BMI = Weight (kg) / Height (m)². Any measurements in other units will be converted to kilograms and meters prior to the calculation. Weight (kg) = weight (lb)/2.2. Height (m) = height (inches)*0.0254.

4.4.3 Prior and Concomitant Medication

A prior medication is any medication taken prior to the first study drug administration. A concomitant medication is any medication that is taken after the first study drug administration. Prior and concomitant medications will be coded using the current version of the World Health Organization classification for therapeutic class and drug name (WHO Drug Dictionary Enhanced).

4.4.4 Efficacy Variables

4.4.5 Safety Variables

The safety and tolerability of eteplirsen will be assessed through:

- A review and evaluation of the frequency and severity of AEs, serious adverse events (SAEs), and discontinuations due to AEs. Adverse events are coded using MedDRA (version 17.1) and are reported by the primary System Organ Class (SOC) and Preferred Term (PT) Name.
 - Adverse events will be classified as treatment-emergent AEs (TEAE) and non-treatment-emergent AEs. TEAEs are those events that develop or worsen during the on-treatment period through 28 days after the last dose of eteplirsen. Non-emergent AEs are those that develop during the pre-treatment period or greater than 28 days after treatment completion.
- Safety laboratory tests (hematology, coagulation, serum chemistry assays and urinalysis, including kidney injury molecule-1 [KIM-1]).
- Vital signs.
- Physical examinations.
- 12-lead electrocardiograms.
- Echocardiogram.

4.5. Randomization and Blinding

This is an open-label study, therefore all patients will receive eteplirsen.

5. STATISTICAL METHODS

5.1. Sample Size

There is no formal sample size calculation. The sample size is based on qualitative considerations and is sufficient to provide safety evaluation of eteplirsen in the studied population. Approximately 20 patients will be enrolled in this study.

5.2. Analysis Population

5.2.1 Safety Population

The safety population will include all subjects who received at least one dose of eteplirsen.

5.3. Handling of Missing Data

[figure not shown]
Imputation of missing data will not be performed unless otherwise specified. Descriptive statistics will be based upon reported data.

5.4. Conventions

5.4.1 Covariates

Analyses will not be adjusted for covariates.

5.4.2 Multiple Testing

5.4.4 Imputation of Incomplete Dates for Concomitant Medications and Adverse Events

An incomplete date occurs when the exact date at which an event occurred or ended cannot be obtained from a subject. Incomplete dates will be imputed as follows:

- For partial or missing medication dates, the medication will be classified as a concomitant medication unless the available part of the date indicates it is not possible for the drug to be concomitant. For example, if only the year for the stop date is available and the year is prior to the year of dosing, the medication would be classified as a prior medication.
 - For partial or missing adverse event dates, the event will be classified as treatment-emergent if the month and/or year are on or after the initiation of eteplirsen and within 28 days of the last dose of eteplirsen, or if it is not possible to determine whether the adverse event date is on or after the initiation of eteplirsen and within 28 days of the last dose of eteplirsen.
- For the purpose of calculating the duration of an adverse event with a missing day but known month and year, the first of the month will be used for all start dates and the end of the month will be used for all end dates (where applicable). For example 01MMMYYYY will be used for UNMMYYYY for start date and 31JANYYYY for UNJANYYYYY (actual value will be based on the month recorded).

5.4.5 Presentations Over Time

For endpoints that are collected serially over time (i.e. laboratory tests, efficacy assessments), events will be assigned to a time-point based upon the eCRF page the event was reported on (nominal time).

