10.3.3. Clinical Laboratory Evaluations

The following routine clinical laboratory tests will be collected at the time points specified in Section 2 and analyzed by an accredited central laboratory selected by the Sponsor and prepared according to the Laboratory Manual provided for the study:

Chemistry: Sodium, chloride, potassium, calcium, glucose, creatinine, blood urea

nitrogen (BUN), albumin, uric acid, total bilirubin, alkaline phosphatase, amylase, alanine aminotransferase (ALT), aspartate aminotransferase (AST), gamma-glutamyl transferase (GGT), lactase dehydrogenase (LDH), C-reactive protein (CRP), creatine kinase

(CK), and serum cystatin C

Hematology: Red blood cells (RBCs), total white blood cells (WBCs), hemoglobin,

hematocrit, neutrophils, lymphocytes, monocytes, eosinophils,

basophils, platelets, and abnormal cells

Coagulation Screen: Prothrombin time, International Normalized Ratio (INR), and

activated partial thromboplastin time (aPTT)

Urinalysis: pH, specific gravity, protein, glucose, ketones, cytology, hemoglobin,

and kidney injury molecule-1 (KIM-1)

Any value outside of the current reference ranges for the laboratory performing the test will be flagged on the laboratory results. The Investigator will determine whether abnormal assessment results are clinically significant (CS) or not clinically significant (NCS). Clinical significance is defined as any variation in assessment results that has medical relevance resulting in an alteration in medical care. If clinically significant deterioration from baseline levels is noted, the Investigator will continue to monitor the patient with additional assessments until:

- Values have reached normal range and/or baseline levels; or
- In the judgment of the Investigator together with the Sponsor's Medical Monitor, abnormal values assessed to be not related to the administration of investigational

product or other protocol-specific procedures, and additional assessments are not medically indicated.

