5.4.6 Definitions and Terminology

Study Day

Study day will be defined as Event Date – Study Day 1 + 1

Study Day 1

Day 1 is defined as the date of first dose of eteplirsen at the Week 1 visit during the 4658-204 Study.

Days on Study

Days on Study is the number of days from Study Day 1 to the date of study completion or early termination as recorded on the END OF STUDY VISIT CRF.

Days on Study Drug

Days on Study Drug is the number of days from the date of first dose to the date of the last dose of the specific study medication as recorded on the STUDY DRUG ADMINISTRATION CRF.

Planned Number of Infusions

The planned number of infusions will be based on the subject's last local site visit. The subject will be expected to receive an infusion once weekly up until their last local site

visit. If a subjects completes 100 local site visits and then completes or discontinues the study the planned number of infusions will be 100.

Treatment Group

All subjects received 30 mg/kg weekly of eteplirsen and will be analyzed in the same group.

Time Since DMD Diagnosis

The time since DMD diagnosis, in months, will be calculated as Month and Year of first dose – Month and Year of diagnosis

Treatment-Emergent Adverse Event

An AE is considered treatment-emergent if it occurs on or after the initiation of the first dose of eteplirsen and within 28 days of last dose.

Treatment Related Adverse Event

A treatment-related AE is any adverse event reported on the CRF that is marked as definitely, probably or possibly related to study drug. Additionally, it is assumed that an AE without a relationship is treatment-related.

Treatment-Emergent Laboratory Abnormality

[figure not shown]
A treatment-emergent laboratory abnormality is defined as any laboratory abnormality (as defined in section 5.5.7.2) that occurs following the initiation of eteplirsen which was not present at Baseline.

Prior Medication

A prior medication is any medication taken prior to the first study drug administration.

Concomitant Medication

A concomitant medication is any medication that is taken on or after the first study drug administration.

Final Analyses

An analysis will be performed once all subjects complete their End of Study visit and the resulting clinical database has been cleaned, quality checked and locked through the data cut.

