5.5.7.2. Laboratory Measurements

Descriptive statistics for continuous hematology, clinical chemistry, urinalysis, and coagulation laboratory measurements will be presented by time point. Summary statistics for each lab parameter and time point as well as the change from Baseline to the time point will be displayed. For each numeric laboratory parameter, box plots of values over time will be generated. A shift table will compare N (%) of low, normal, and high status of the lab values at Baseline to their worst value post-Baseline through Week 96. A table summarizing the frequency and percent of subjects meeting the predefined markedly abnormal criteria at each visit will be presented. The predefined markedly abnormal criteria are defined below in Tables 3-1, 3-2, and 3-3. All laboratory values will be displayed in a data listing.

Table 3-1 Predefined Markedly Abnormal Hematology Laboratory Values

Test	Unit	Markedly Abnormal Criteria
Hematocrit	1	< LLN
Hemoglobin	g/L (or mmol/L)	< LLN
Red blood cell count	T/L	< LLN
White blood cell count	count/L	$>1.5 \times ULN \text{ or } < LLN$
Platelet count	10^3/L	< 150 or < 200 with a decrease of at least 100
Basophils (abs)	count/L	> ULN or < LLN
Eosinophils (abs)	count/L	> 1.5xULN or < LLN
Lymphocytes (abs)	count/L	< LLN
Monocytes (abs)	count/L	< LLN
Neutrophils (abs)	count/L	>1.5 × ULN or < 1000

ULN = upper limit of normal

LLN = lower limit of normal

abs = absolute

Table 3-2 Predefined Markedly Abnormal Chemistry Laboratory Values

		Predefined	Change	
Test	Unit	Decrease	Increase	Markedly Abnormal Criteria
Fasting blood glucose*	mmol/L	3.1	3.2	
Urea (BUN)	mmol/L			Value >1.5 × Baseline Value AND > ULN
Creatinine	μmol/L		35	Value >1.5 × ULN
Sodium	mmol/L	8	8	
Potassium	mmol/L	1.1	1.0	Value >5.5 mmol/L or < 3 mmol/L
Chloride	mmol/L	9	8	
Uric acid	μmol/L			>1 × ULN
Calcium#	mmol/L	0.30	0.30	
Total cholesterol	mmol/L		1.73	
AST (SGOT)	U/L			Value ≥3 × Baseline Value
ALT (SGPT)	U/L			Value ≥2 × Baseline Value
Gamma GT (GGT)	U/L			Value >3 × Baseline Value OR > ULN
Alkaline phosphatase	U/L			Value >1.5 × ULN
Total protein@	g/L	11	10	
Albumin	g/dL	1 g/dL decrease or	1 g/dL increase	Value < LLN or > ULN
Total bilirubin ^{&}	μmol/L		10	Value >1.5 × ULN
LDH	U/L			Value ≥2 × Baseline Value
Creatine phosphokinase	U/L			Value ≥2 × Baseline Value
Triglycerides	mmol/L	_	2.88	
Cystatin C	mg/L			>ULN

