5.5.7.3. Vital Signs

Vital sign parameters will be presented by time point, summarizing the actual values and change from Baseline to each on-treatment time point using descriptive statistics. A table summarizing the frequency and percent of subjects meeting the predefined markedly abnormal criteria at each visit will be presented. The predefined markedly abnormal criteria are defined below in Table 4. Vital signs data will be presented in the data listings.

Table 4 Predefined Markedly Abnormal Vital Sign Values

Variable	Units	Markedly Abnormal Criteria Lower limit	Markedly Abnormal Criteria Upper limit
Systolic blood pressure	mm Hg	<80	>130
Diastolic blood pressure	mm Hg	<40	>90
Pulse Rate	beats/min	<50	>130
Temperature	°C		≥40

5.5.7.4. 12-Lead ECGs

Electrocardiogram (ECG) parameters will be presented by time point, summarizing the actual values and change from Baseline to each on-treatment time point using descriptive statistics. A shift table will compare N (%) of ECG status at Baseline to the worst reported value through Week 96. A table summarizing the frequency and percent of subjects meeting the predefined markedly abnormal criteria at each visit will be presented. The predefined markedly abnormal criteria are defined below in Table 5. ECG data will be provided in a data listing.

Table 5 Predefined Markedly Abnormal Electrocardiogram Values

Variable	Units	Lower limit of normal	Upper limit of normal	Age Group (yrs)	Markedly Abnormal Criteria
Heart Rate	beats/min	50	120		
QTcF Interval	msec			All	Screening Visit >450
				<12	>480
				≥12	>500
				All	<320
					Increase >60
QRS Interval	msec			<12	IVCD or any QRS conduction disturbance
					with a QRS >110ms
				≥12	IVCD or any QRS conduction disturbance
					with a QRS >120ms
PR Interval	msec			<12	>190
				≥12	>220

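### The markedly abnormal tables run by visit only, with no any-post-Baseline row, so a patient who crosses a threshold only on an unscheduled test may go uncounted

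*SAP*

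**What the plan says.** SAP 5.4.5 covers results collected serially and names laboratory tests and efficacy assessments. For these, "events will be assigned to a time-point based upon the eCRF page the event was reported on (nominal time". It gives no date window and does not mention unscheduled or repeat results.

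SAP 5.5.7.2 sets thresholds in Tables 3-1 to 3-3 and describes one tabulation that uses them: "A table summarizing the frequency and percent of subjects meeting the predefined markedly abnormal criteria at each visit will be presented". Vital signs (5.5.7.3), ECG (5.5.7.4) and ECHO (5.5.7.5) follow the same format. None of the four describes a row for any time after Baseline.

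Off-schedule laboratory data are expected. Protocol 10.3.3 says: "If clinically significant deterioration from baseline levels is noted, the Investigator will continue to monitor the patient with additional assessments until" values recover, or the Investigator and Medical Monitor judge them unrelated and further testing unnecessary.

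Other outputs bear on the point:

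- The laboratory shift table compares "low, normal, and high status of the lab values at Baseline to their worst value post-Baseline through Week 96".
- For ECG, "A shift table will compare N (%) of ECG status at Baseline to the worst reported value through Week 96".
- "All laboratory values will be displayed in a data listing".
- SAP 5.4.6 defines a treatment-emergent laboratory abnormality as "any laboratory abnormality (as defined in section 5.5.7.2) that occurs following the initiation of eteplirsen which was not present at Baseline", but no table described in 5.5.7.2 uses that definition.

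Protocol 7.3.1 makes the incidence of laboratory abnormalities a safety endpoint. Protocol 13.1 sends all available data to tables as well as listings. SAP section 6 declares one departure from the protocol, on Holter data.

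**The concern.** The plan generates results for which its main abnormality table defines no row. A repeat test ordered because a patient is getting worse is among the values most likely to cross a threshold, yet a table indexed by scheduled visit has no stated place for it.

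Incidence is a per-patient, any-time quantity. The SAP's own thresholds are tabulated only visit by visit, so the named endpoint is not directly reported under those criteria even for scheduled values. If unscheduled values are also left out, a reader of the study report could see no flagged patient for a parameter on which one patient did qualify. In a safety study of this size that changes the message.

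**Working it through.** The documents give no abnormality rate, power or expected count for this point, so there is no stated figure to reproduce. The check follows the rules through the documents and then asks what one patient is worth.

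**1. Scheduled laboratory visits** (Protocol Tables 2 and 3; SAP Tables 1 and 2). After Baseline/Week 1 they fall at Weeks 4, 8, 12, 24, 36, 48, 72 and 96, which is 8 visits through Week 96. The safety extension adds Weeks 120 and 144, and there is an End of Study draw. The gaps are 3, 4 and 4 weeks up to Week 12, then 12, 12 and 12 up to Week 48, then 24 weeks each. An abnormality can arise and resolve between draws.

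**2. When a patient is lost.** All three must hold: the threshold is crossed on an unscheduled test, it is crossed at no scheduled visit, and the unscheduled result is not entered under a visit row. Illustration with assumed values: ALT is 1.8 times Baseline at the visit and 2.5 times on repeat. The Table 3-2 criterion is at least 2 times Baseline, so only the repeat qualifies.

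**3. What the other outputs recover.**

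| Output | Could show the unscheduled value? | Limit |
|---|---|---|
| Laboratory shift table | Yes, worst value | Low/normal/high only; stops at Week 96 |
| ECG shift table | Yes, worst value | Stops at Week 96 |
| Vital signs, ECHO | No worst-value table described | |
| AE tables | If medical care changed (Protocol 11.2.1) | Coded terms, not the SAP thresholds |
| Laboratory listing | Yes | Not an incidence |

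The shift table cannot show baseline-relative criteria: ALT, LDH and creatine phosphokinase at 2 times Baseline or more, AST at 3 times or more. A patient already high at Baseline whose ALT doubles stays high-to-high. Weeks 120 and 144 lie outside the table.

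**4. By-visit rows do not give incidence.** Suppose, for illustration, that 1 of 20 patients is flagged at each of the 8 visits through Week 96. The number ever flagged could be 1/20 = 5% (the same patient throughout) or 8/20 = 40% (a different patient each time).

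**5. Value of one patient.** With N about 20 (SAP 5.1), 1/20 = 5.0 percentage points. Exact (Clopper-Pearson) 95% intervals are 0 to 16.8% for 0/20 and 0.1 to 24.9% for 1/20.

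**6. Range under assumptions.** Let p be the true proportion ever markedly abnormal and s the share of those seen only off-schedule. Neither is in the documents. The expected number missed is 20ps, and the chance of missing at least one is 1 − (1 − ps)^20.

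| p | s | Expected missed | Percentage points | Chance of missing at least one |
|---|---|---|---|---|
| 10 to 30% | 0 | 0 | 0 | 0 |
| 10% | 25% | 0.5 | 2.5 | 40% |
| 20% | 25% | 1.0 | 5.0 | 64% |
| 30% | 50% | 3.0 | 15.0 | 96% |

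**The case against.** The strongest reply is that the documents are silent and do not exclude anything. A reader might infer that SAP 5.4.5 removes unscheduled values by rule and so biases incidence downward. No text says that. Protocol 13.1 points to inclusion, and SAP section 6 declares no departure from it. The eCRF is not available, and an extra draw might be entered on a visit page. SAP numbering also skips 5.4.3 and 5.4.7, so a convention on this could have stood there. This stands: the point can only be that such patients may be missed.

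Second, Protocol 10.3.3 tests follow a deterioration already noted, sometimes at a scheduled visit that is counted. Because that section ties clinical significance to a change in care, many such events are also AEs under Protocol 11.2.1, and several laboratory-related areas have special-interest summaries in SAP 5.5.7.1.1. This stands in part. AEs are a separate endpoint in Protocol 7.3.1, and they do not report who met the SAP thresholds.

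Third, SAP 5.4.5 names only laboratory tests and efficacy assessments. Carrying the point to vital signs, ECG and ECHO rests on their by-visit table format, not on that rule. This stands.

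**Conclusion.** The point holds as a gap in the described analysis, not as a demonstrated undercount. In the SAP text available, the markedly abnormal criteria appear only in by-visit tables. Nothing says how unscheduled results enter them, and nothing reports a per-patient any-time count. Shift tables and AE reporting compensate only in part.

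The size cannot be calculated from the documents. It is zero if every affected patient also qualifies at a scheduled visit, or if unscheduled values are in fact entered under visit rows. Each patient missed is 5 percentage points. The 0 to 15 point range above rests wholly on assumed p (10 to 30%) and s (0 to 50%).

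A reader might also divide an assumed episode length by the 24-week gap (4/24 = 17%) and take the remaining 83% as the share lost. That measures how sparse the schedule is. An episode between draws is seen in no sample unless someone orders a test, and the documents give no rate of unscheduled testing and no episode durations.

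The change is worth making because it improves the reporting of a named endpoint at little cost, even though the study is descriptive and all laboratory values are listed.

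**What to change.** - Add to the laboratory markedly abnormal table a row counting patients who meet each criterion at any time after Baseline, unscheduled results included. Add the same row to the vital sign, ECG and ECHO tables for consistency.
- Keep the by-visit summaries on scheduled values.
- State that the worst-value shift tables include unscheduled results.

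Assigning each unscheduled result to the nearest scheduled visit is a weaker alternative. With 24-week gaps it could relabel a result by up to 12 weeks, and the by-visit flags would then depend on how often a patient was tested.

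The cost is SAP wording and one derived flag per criterion. The downside is that patients tested more often have more chances to be flagged, which a table footnote should say.
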